Aim 1: Discover Phase (3 months). Using iterative and participatory methods, we will interview up to 15 clinicians from FHQCs affiliated with the WWAMI region Practice Research Network (WPRN, a collaborative group of primary care practices through the states of Washington, Wyoming, Alaska, Montana and Idaho to facilitate innovative community-based research), and observe them in routine practice to identify usability challenges. Contribution to the Center: Data from this phase will be used to inform the Typology of EBPI Targets.

Aim 2: Design/Build Phase (6 months) After identification of potential targets, the research team will work via Zoom teleconferencing with the original clinicians from the discover phase and 0-5 new clinicians to engage in a rapid cycle of iterative prototype development and testing (e.g., storyboarding, paper prototypes) of BA modifications. The build of these modifications will include the development of intervention prototypes for user testing and refinement with input from these care managers. Contribution to the Center: Data from this phase will be used to inform the Matrix of EBPI Modifications.

Aim 3: Test Phase (15 months). We will test and compare the BA modification (modBA) to usual care in a small non-randomized trial. We will assign all provider teams (therapist & care manager(s)) in the clinic to use modBA with 10 patients per team for a total of 40 patients. We will then compare patient outcomes for those receiving modBA vs. 40 patients receiving usual clinic care. **H1:** Modifications developed in the Design/Build phase for targets identified in the Discover Phase will result in better usability (System Usability and User Burden Scales) compared to usual care.

H2: modBA will be more effective than usual care on improving clinical outcomes of functional disability (Sheehan Disability Scale [SDS]), change in depression symptoms over time (PHQ-9 total score), and change in anxiety symptoms over time (GAD-7 total score).

1.6 Study design. Provide a one-sentence description of the general study design and/or type of methodology.

Your answer will help HSD in assigning applications to reviewers and in managing workload. Examples: a longitudinal observational study; a double-blind, placebo-controlled randomized study; ethnographic interviews; web scraping from a convenience sample of blogs; medical record review; coordinating center for a multi-site study.

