when to use BA in specific clinical situations. The Therapists and Care Managers of some clinics in the BVHC network have already implemented this modified approach, and the goal is to have all clinics in the network learn and use the model. The Therapists and Care Managers will receive additional training and guidance from the study team to achieve this modification, but the patients' clinical care visits will not change. During the additional training, UW and Stanford study staff members will provide consultation on BVHC patient cases in order to provide support for any cases where BVHC clinicians are having difficulty using BA. During these discussions, no staff from the UW or Stanford team will ever know any identifiable information about the patients. However, both UW and Stanford staff members will have access to clinician participants' identifiable information from training/support activities with the clinicians. We will use pre-existing clinic measures to collect patient outcome data for patients whose providers are using the modified BA model. We will also collect patient outcomes using the same pre-existing clinic measures for patients whose providers are providing usual care. We will then compare outcome data for each type of care. A total of 11 clinicians and 80 patients will be recruited for Phase 3.

Clinician Procedures:

Clinician training in BA. UW team staff will train clinicians in modified Behavioral Activation elements per the protocol used by the AIMS Center, which includes training in basic brief treatment skills, therapeutic elements of the intervention and therapy process. The training will also include modifications developed via clinician/research staff co-design in Phase 2.

Note: These modifications will be developed in Phase 2, and new materials will be submitted to the IRB prior to beginning Phase 3.

Training will be followed by simulated case training. Once clinicians finish the training and begin using the modified BA with patients, we will use a self-report checklist and open-ended questions regarding the use of modified BA to measure clinicians' adherence to the model.

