Two types of data will be collected, clinician assessment of intervention usability, and clinician ability to learn the intervention and maintain competency. To measure intervention usability, clinicians will complete the AIM, FIM, IAM, the User Burden Scale and the System Usability Scale, which are core measures for this Center. These measures will be administered both pre- and post-. Clinicians may also be asked to complete exit interviews regarding their experience using the BA task-sharing model. These interviews may be video-recorded (with clinician consent) for later review.

To measure sustained competency, clinicians will use a self-report checklist of task-sharing BA components with each patient to ensure they are adhering to the model. Clinicians will also complete qualitative questions regarding model adherence at the end of the study.

We will conduct 3-month follow up interviews with clinicians to ask if they are still using the task sharing model, if they are using all aspects of the model, and if they have made any modifications to the model. These interviews may be video-recorded (with clinician consent) for later review.

Clinician procedures are summarized here:

- Complete updated consent form
- Complete full BA task-sharing training starting in January 2020

- 6 synchronous sessions (about 1 hour each)
- Complete asynchronous material in between sessions
- Staff will be paid \$50 for each of the 6 synchronous sessions they attend
- Complete pre-trial usability questionnaires re: BA task-sharing model, for which they will be paid \$25
- After BA task-sharing training is complete, begin using the model with clinic patients (target of 10 patients per clinic)
- Use a self-report checklist of task-sharing BA components with each patient to ensure they are adhering to the model
- Complete post-trial usability questionnaires re: BA task-sharing model, for which they will be paid \$25
- Possibly complete exit interviews re: their experience using the BA task-sharing model, for which they would be paid \$50. These interviews may be video-recorded (with clinician consent) for later review.
- Complete a 3-month follow up interview to report if/how they are still using the modified BA model, for which they will be paid \$50. These interviews may be video-recorded (with clinician consent) for later review.

Patient Procedures

Patient eligibility.

Patient participants will be identified through each clinic's electronic health record.

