Aim 1: Discover Phase (3 months). Using iterative and participatory methods, we will interview 10 clinicians from FQHCs affiliated with the WWAMI region Practice Research Network (WPRN, a collaborative group of primary care practices through the states of Washington, Wyoming, Alaska, Montana and Idaho to facilitate innovative community-based research), and observe them using PST-PC to identify usability challenges.

[figure not shown]
Contribution to the Center: Data from this phase will be used to inform the Typology of EBPI Targets.

Aim 2: Design/Build Phase (6 months) After identification of potential targets, the research team will work with the original 10 clinicians to engage in a rapid cycle of iterative prototype development and testing (e.g., storyboarding, paper prototypes) of BA modifications. The build of these modifications will include the development of intervention prototypes for user testing and refinement with input from these care managers.

Contribution to the Center: Data from this phase will be used to inform the Matrix of EBPI Modifications.

Aim 3: Test Phase (15 months). We will test and compare the BA modification (Task Sharing) to usual care in a small non-randomized trial. We will assign all provider teams (therapist & care manager(s)) in the clinic to use Task Sharing with their patients. We will then compare patient outcomes for those receiving Task Sharing vs. patients receiving usual clinic care. H1: Modifications developed in the Design/Build phase for targets identified in the Discover Phase will result in better usability (System Usability and User Burden Scales) compared to usual care. H2: Task Sharing will be more effective than usual care on improving clinical outcomes of functional disability (Sheehan Disability Scale [SDS]), change in depression symptoms over time (PHQ-9 total score), and change in anxiety symptoms over time (GAD-7 total score).

This study directly addresses IOM report recommendation 3-1: conduct research on psychosocial intervention elements and NIMH SP 4.1 Improve efficiency and effectiveness of existing mental health services.

SIGNIFICANCE

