between modified BA and usual care will be plotted using a dotplot and tested using a *t*-test using the SUS and UBS as dependent variables. **H2: Fidelity/Competence:** A similar strategy (dotplot, *t*-test) will be used with number of hours to reach certification. Number of sessions with fidelity scores <4 (“good”) will be summarized as proportions, both by clinician and by treatment. Between-treatment differences will be tested with a 2-sample proportion test. (Future analyses with larger sample size will use a generalized linear mixed model approach to account for the nested data^{89,90}.) **H3: Patient Reported Outcomes.** Histograms and kernel density estimates will be plotted by treatment condition to explore differences on depression outcomes (PHQ-9 total score) and overall daily functioning (SDS). Descriptive statistics (*M* and *SD*) will also be examined by clinician and by treatment, using Cohen’s *d* as an effect size summary. A *t*-test will be used to examine treatment differences in patient outcomes. Of ultimate interest is whether the modified treatment has its impact on patient outcomes through enhanced usability and clinician fidelity. We will use graphical summaries of the data to explore the relationships that are consistent with mediation (e.g., correlation of usability with patient outcomes [b pathway], and treatment differences on patient outcomes with fidelity partialled out [c’ pathway]). The primary focus here is whether the data and relationships appear consistent with mediation, as opposed to a formal test, which will be dramatically under-powered.

Power and Sample Size. Sample sizes for Aims 1 and 2 were based on estimates from the UCD literature on necessary number of participants to capture critical design information, where the recommendation is 5-10 end users. As Aim 3 is focused on gathering information (feasibility, recruitment and retention rates, response and attrition rates, etc.) for a future R01 application, the sample size was set primarily for practical reasons and used estimated effect sizes, rather than being driven by hypothesis testing.

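### H1 compares clinician usability scores with usual care, but no usual-care SUS or UBS rating is scheduled under the non-randomized design

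*Combined protocol and SAP*

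**What the plan says.** **Hypothesis.** H1, in section 1.5 (Aim 3) and again in the Specific Aims of the research plan, is that the modifications "will result in better usability (System Usability and User Burden Scales) compared to usual care". The Project Summary lists usability first among three comparisons with usual care.

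**Analysis.** Under H1 in Data analysis, differences in clinician-reported usability "between modified BA and usual care will be plotted using a dotplot and tested using a" *t*-test, with SUS and UBS as the dependent variables.

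**Design.** The Specific Aims state: "We will test and compare the BA modification (Task Sharing) to usual care in a small non-randomized trial". Section 1.5 adds: "We will assign all provider teams (therapist & care manager(s)) in the clinic to use modBA".

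**Clinician data.** The narrative in section 5.1 (Phase 3, Clinician Procedures) lists SUS and UBS among the usability measures and says "These measures will be administered both pre- and post", without naming what is rated. The itemised list in the same section does name it: "Complete pre-trial usability questionnaires re: BA task-sharing model, for which they will be paid" $25, and "Complete post-trial usability questionnaires re: BA task-sharing model, for which they will be paid" $25.

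**Usual-care data.** Section 5.1 (Phase 3 Testing) says "We will also collect patient outcomes using the same pre-existing clinic measures for patients whose providers are providing usual care". The Patient Procedures list specifies PHQ and GAD for both groups of patients. No clinician form is listed for usual care.

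**The concern.** The contrast in H1 needs SUS and UBS scores under two conditions. The clinician procedures appear to collect them under one, twice. An analyst following the Data analysis section would then have either nothing to put in the usual-care column, or pre-trial ratings of the modified model standing in for it. The second would mislead: two ratings of the same model show how opinion of it shifts with experience, and say nothing about whether it is easier to use than the care it replaces. The pilot is meant to inform a larger trial of modified BA against usual care, so a mislabelled usability contrast would carry forward into that trial.

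**Working it through.** The documents give no alpha, power, effect size or SD for H1, so there is no figure to reproduce. The check is who completes SUS and UBS, when, and about what.

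**1. Every place where a usability rating could arise**

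| Place | Rater | Object rated |
|---|---|---|
| 5.1 Phase 2, and Phase 2/Aim 2 in the research plan | Design-phase clinicians | Prototypes of the modification |
| 5.1 Phase 3, clinician narrative | Phase 3 clinicians, pre and post | Not named |
| 5.1 Phase 3, itemised list, pre-trial | Phase 3 clinicians | BA task-sharing model |
| 5.1 Phase 3, itemised list, post-trial | Phase 3 clinicians | BA task-sharing model |
| 5.2 Data variables, Phase 3 | Phase 3 clinicians | Listed under intervention usability; no usual-care form |
| 5.1 Phase 3, usual-care side | None | Patient outcomes only |
| Research plan, Clinician data collection | Clinicians | Not named |

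Entries that name usual care as the object rated: 0.

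**2. Could usual-care teams supply the scores?** Section 1.5 gives 10 patients per team and 40 in total, so 40 / 10 = 4 teams, all assigned to the modified model. Section 5.1 implies that usual-care providers exist elsewhere in the network, but assigns them no usability form.

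**3. Forms available**
- 11 clinicians (sections 2.1, 4.1, 5.1): 11 × 2 = 22 per scale.
- 13 clinicians (maximum in the section 2.7 table): 13 × 2 = 26 per scale.

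These are ceilings, and all of the forms concern the modified model.

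**4. Where the two-condition test seems to come from.** The Test phase paragraph of the research plan has therapists randomized, in a sentence that names only one arm, and the Timeline speaks of training in two interventions. The between-condition *t*-test fits that layout. It conflicts with the non-randomized design, and even there the clinician data paragraph does not say what is rated.

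**5. Precision if clinicians rate current care first and the modified model afterwards.** The half-width of the 95% CI for the paired mean difference, in units of the SD of the differences, is t(0.975, n−1)/√n:
- n = 11: 2.228 / 3.317 = 0.67
- n = 13: 2.179 / 3.606 = 0.60

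Both assume complete pairs and ignore correlation within provider teams, so they are best cases.

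**The case against.** The strongest reply is that the section 5.1 narrative leaves the object of the pre rating open, that the list naming the task-sharing model is introduced as a summary, and that the description of the scales is deferred to a Methods Core text outside these documents. The pre rating might therefore have been meant as a usual-care baseline. That reading is not impossible, but the only wording that names an object rules it out, and no other text restores it. The list also places the pre-trial form after training (judged from item order), which is late for a rating of current care.

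A second reply is that Aim 3 is expressly descriptive and its sample size was set for practical reasons. This limits the inferential damage, and the point here is not about power. A dotplot or effect size still needs scores on both sides.

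A third is that the mismatch is left over from another design, so reconciling the text would cure it. It would not: section 1.5 repeats the usual-care H1 within the non-randomized text.

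One objection does stand. If providers not yet trained in the model could be enrolled, they could complete SUS and UBS about usual care, which would keep a concurrent comparator. It would be small and non-randomized. As an illustration, with two-sided alpha 0.05 and 80% power (both assumed), a 6 versus 5 split detects about 1.91 between-clinician SDs and a 7 versus 6 split about 1.71.

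**Conclusion.** The concern holds. Under the non-randomized design and the itemised clinician procedures, the H1 contrast has no scheduled usual-care score: 0 usual-care ratings against at most 22 or 26 forms per scale about the modified model. The first Test-phase hypothesis therefore cannot be answered as written, even descriptively, and this must be corrected. The conclusion rests on reading the itemised list as defining what is rated, and on the non-randomized text being the operative design. The PHQ-9 and GAD-7 comparisons are untouched.

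A related mismatch is noted but not counted in this judgement. The research plan has experts rate recorded sessions and compares fidelity between treatments, while sections 5.1, 5.2 and 5.14 provide only clinician self-report on the modified model.

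**What to change.** First reconcile section 1.5 and the Specific Aims with the Test phase paragraph and Timeline: state whether clinicians are randomized and whether any enrolled clinician delivers usual care. Then choose one of the following.

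**(a) Collect a usual-care rating.** Before training, each clinician completes SUS and UBS about their current way of delivering care and records whether they already use the task-sharing model. After the trial, they complete both scales about the modified model. Replace the between-condition *t*-test with the paired within-clinician difference and its 95% CI, described as a pre/post contrast that mixes condition with time, training and co-design involvement.

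The cost is a changed instruction, one extra item and a time point ahead of training. Either the pre-trial rating of the modified model is given up, or both scales are completed an additional time, within the 20-minute survey limit in section 10.1 and possibly with a further payment. The baseline will not be clean, because some clinics already use the model (section 5.1) and some clinicians helped design it (section 4.2). The estimate will be imprecise (half-width at best 0.60 to 0.67 SD of the differences). This rating cannot be obtained once clinicians have been trained.

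**(b) Restate H1** as pre-to-post change in usability ratings of the modified model, removing the comparison with usual care, and align the analysis text and Project Summary. This is little more than a one-sentence change and gives up the usability comparison.

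If untrained usual-care providers can be enrolled, scheduling the same scales for them is a further route, with the limits given above.

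For the secondary point, unless usual-care sessions will actually be rated, replace the between-treatment fidelity tests with a descriptive adherence summary for the modified model, and state that the mediation summary adjusting for fidelity cannot be made across conditions. That gives up the competence comparison in the Project Summary.

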Participants must be 18 years old or older, suffering from mild to moderate depression. The site champion will identify potential participants from their electronic health records (EHRs) who score between 10 and 20 on the PHQ-9. Patient procedures include:

- Up to 40 patients who are already receiving care at BVHC will receive care via the BA task-sharing model
- We will also include a sample of up to 40 other patients who are already receiving care at BVHC (but not yet receiving care via the modified BA model) who will continue to receive their usual care
- Patients will complete weekly PHQ and GAD (already being collected by BVHC as part of usual care). This includes both the patients who are receiving care via the BA task-sharing model and those who are receiving care without the model
- We will collect historic patient data (PHQ and GAD, already collected by BVHC and agreed to by patients) for all patient participants. This includes both the patients who are receiving care via the BA task-sharing model and those who are receiving care without the model.
- We will collect 3-month follow up patient data (PHQ and GAD, already collected by BVHC and agreed to by patients) for all patient participants. This includes both the patients who are receiving care via the BA task-sharing model and those who are receiving care without the model.
- We will ask up to 10 patients who received care via the BA task-sharing model to complete exit interviews to give their perspective on the care they received. Patients will be consented for these

interviews, as we will then be asking patients to complete research activities that are beyond activities already completed during their usual care. Patients will be paid \$25 for the exit interviews.

- 5.2 Data variables.** Describe the specific data you will obtain (including a description of the most sensitive items). If you would prefer, you may upload a list of the data variables to the **Supporting Documents** SmartForm instead of describing the variables below.

Clinician Data:

Phase 1 & 2 qualitative clinician interviews:

We request flexibility in qualitative interviewing questions with clinicians during Phase 1 and 2 which will include:

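### Aim 3 is described as non-randomised, but the patient-outcome analysis names no baseline score, does not say whether it tests a post score or a change score, and omits GAD-7

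*Combined protocol and SAP*

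**What the plan says.** **Allocation.** Section 1.5 (Aim 3) states: "We will test and compare the BA modification (modBA) to usual care in a small non-randomized trial". It assigns all provider teams "in the clinic to use modBA with 10 patients per team for a total of 40 patients". The Specific Aims in the appended research plan agree: "We will test and compare the BA modification (Task Sharing) to usual care in a small non-randomized trial". Section 5.1 (Phase 3 Testing) adds: "The Therapists and Care Managers of some clinics in the BVHC network have already implemented this modified approach". Under Patient Procedures in the same section, "Up to 40 patients who are already receiving care at BVHC will receive care via the BA task-sharing model", and the comparison group is up to 40 other patients in care there, described as "but not yet receiving care via the modified BA model) who will continue to receive their usual care". On this text, arm follows provider team or clinic roll-out.

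**Hypothesis.** H2, worded alike in both sets of aims, covers the Sheehan Disability Scale (SDS) and "change in depression symptoms over time (PHQ-9 total score), and change in anxiety symptoms over time (GAD-7 total score".

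**Analysis.** The Data analysis paragraph on patient-reported outcomes (labelled H3) plans histograms, kernel densities, means and SDs per clinician and per arm, Cohen's d, and a t-test that "will be used to examine treatment differences in patient outcomes". It names the PHQ-9 total score and SDS. It contains no baseline term, no choice between post and change score, and no GAD-7. The only variable partialled out is fidelity, in the exploratory mediation plots. The same section says the emphasis is descriptive rather than inferential.

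**Data.** Section 5.1 already plans historic, weekly and 3-month PHQ and GAD scores in both arms.

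**The concern.** When arm follows team or roll-out, nothing in the design makes the two groups alike at the start. They may differ in severity, in time already spent in treatment, or in who treats them. A t-test or Cohen's d without a baseline term can then mix the starting difference with the effect of the modified model. Because the tested variable is not named, two analysts following the same text could report different effects, possibly of opposite sign. One of the two symptom scales in H2 would have no planned analysis at all.

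**Working it through.** The plan gives no effect size, SD, alpha or power for Aim 3, so there is no figure of its own to reproduce. What follows is algebra on assumed inputs.

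**Definitions.** The index score is the single score taken as a patient's baseline. G is the arm difference (modified BA minus usual care) in mean index score. P is the arm difference in mean post score when there is no true effect. b is the within-arm slope of post on index score. Higher scores are worse.

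- Post-score bias = P
- Change-score bias = P - G
- ANCOVA bias (arm plus index score) = P - bG
- Post minus change = P - (P - G) = G, whatever P is

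**Case 1: the index score carries the whole imbalance, so P = bG.** Assume G = 2 and b = 0.4 to 0.8.

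| | b = 0.4 | b = 0.8 |
|---|---|---|
| Post score | 0.4 x 2 = +0.8 | 0.8 x 2 = +1.6 |
| Change score | 0.8 - 2 = -1.2 | 1.6 - 2 = -0.4 |
| ANCOVA | 0.8 - 0.8 = 0 | 1.6 - 1.6 = 0 |

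With an assumed post SD of 5, the post-score d is 0.8/5 = 0.16 to 1.6/5 = 0.32. For G from 1 to 3, the post-score bias runs from 0.4 x 1 = +0.4 to 0.8 x 3 = +2.4, and the change-score bias from (0.4 - 1) x 3 = -1.8 to (0.8 - 1) x 1 = -0.2.

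**Case 2: the arms differ stably.** Ignoring the entry rule, P = G = 2. The post-score bias is +2, the change-score bias is 0, and the ANCOVA bias is (1 - b) x 2 = +1.2 to +0.4. But patients enter only with a PHQ-9 of 10 to 20 (sections 2.2 and 5.1). One window applied to both arms shrinks the index gap, and part of the stable difference returns at follow-up. I simulated this with stable arm means of 16 and 14, normal true scores and errors, index score rounded and kept within 10 to 20, no true effect, and 2 million draws per arm. With true-score SD 4 and error SD 3, the index gap is 0.68 and the post gap 1.16. The change-score bias is 1.16 - 0.68 = +0.48 and the ANCOVA bias is +0.73. Over SD pairs (4, 3), (3, 3) and (4, 4), the change-score bias is +0.48 to +0.71 and the ANCOVA bias +0.73 to +1.00. Both have the same sign and lie within half a point of each other.

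**Clustering.** Section 1.5's 10 patients per team and 40 patients imply 40/10 = 4 modified-BA teams. The number of usual-care teams is not given; assume 4. The design effect is 1 + (10 - 1) x ICC, and the approximate coverage of a patient-level 95% CI is 2Φ(1.96/√design effect) - 1.

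| Assumed ICC | Design effect | Coverage |
|---|---|---|
| 0.02 | 1.18 | about 93% |
| 0.05 | 1.45 | about 90% |
| 0.10 | 1.90 | about 84% |

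Simulated ANCOVA intervals agree to within about a percentage point.

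**Design text side by side.** Sections 1.5 and 5.1 give 40 + 40 = 80 patients, and both sets of aims say non-randomised. The research plan's Study Overview gives 6 clinicians and 30 patients, and its Phase 3 text has therapists randomised with 5 patients each (6 x 5 = 30); that sentence names only the modified-BA arm. Section 1.5 counts 10 patients per team, whereas the clinician procedures in section 5.1 target 10 per clinic. SDS appears in the research plan's data collection and analysis text but not in the section 5.2 variable list.

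**The case against.** The strongest reply is that this is a declared descriptive pilot, sized for practical reasons, with plots and summaries as the main product. That stands, and it limits the weight of the point. It does not remove it, because a t-test and Cohen's d are still planned and neither is defined.

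A second reply is that the analysis text may belong to the 30-patient plan with randomised therapists. If that design is current, a baseline gap would arise only by chance. This is fair, and it is why the design text has to be settled first. The Specific Aims of that same research plan nevertheless say non-randomised.

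A third is that the plan does not ignore providers. It summarises patient outcomes per clinician, and its fidelity paragraph recognises nesting but leaves the modelling to larger future studies. That also stands. What is missing is an allowance for clustering in the patient-outcome comparison, or a caveat.

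The entry window does limit how far the arms can differ on index PHQ-9. It does not limit GAD-7 or time in treatment, and Case 2 shows that it can itself introduce bias.

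**Conclusion.** The analysis section should be changed, at modest severity. It leaves the tested variable unstated, uses no baseline score in a comparison described as non-randomised, and drops GAD-7 from H2. That post and change comparisons differ by the baseline gap is exact. The sizes shown are not findings about this trial: gap, slope, SDs, ICC and the number of usual-care teams are all assumed.

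Four stronger readings are tempting and are not supported:

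- That the plan commits to raw post scores. It does not say, and a t-test on change scores is not excluded.
- That the arms are in fact imbalanced. The documents report no gap.
- That ANCOVA and change-score results shown together would bracket the true effect, so that agreement would reassure. Under the PHQ-9 10 to 20 window both can err in the same direction while lying close together.
- That the unadjusted d will size the future trial. The sample size text lists feasibility, recruitment, retention, response and attrition as the information sought for the next application, and nowhere says d will be used that way.

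**What to change.** First reconcile the design text: 30 patients with randomised therapists against 80 patients without randomisation; 10 patients per team against 10 per clinic; and SDS in the analysis against its absence from section 5.2. Then, in the Data analysis section:

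1. State the tested variable in line with H2 and add GAD-7.
2. Report index PHQ-9 and GAD-7 by arm, using one index rule named before data transfer that works in both arms. The research plan's pre-treatment assessment does not supply one for patients already in care.
3. For each scale, add one pre-named baseline-adjusted estimate with a 95% CI: ANCOVA on arm and index score, or a longitudinal model of the weekly scores. Read it at the same time after index in both arms. The change-score difference can be an optional sensitivity result.
4. State that neither estimate removes provider, clinic or other unmeasured differences, that the entry window can bias both in the same direction, and that agreement between them does not show absence of bias.
5. Allow for clustering by provider team once the unit is settled, or state that patient-level intervals may be too narrow.

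The plots, means and Cohen's d can stay as description.

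The cost is a few sentences and a little more analysis work, with no new PHQ-9 or GAD-7 collection. Because the clinic de-identifies data before sending them (section 5.7), it would need to supply score timing, for example as days from index, and a coded team label. Intervals that allow for clustering will be somewhat wider.
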